3.8 Justification of choice of study population

We will include participants who are ≥ 18 years old, smoke > 5 cigarettes a day since > 1 year, and are willing to quit smoking within the next three months. We will restrict to smokers smoking 5 or more cigarettes per day in order to randomize smokers with sufficient tobacco cigarette exposure to be able to adequately detect harmful components of tobacco cigarettes in the urine and to smokers who are expected to need nicotine substitution by ENDS in order to stop smoking cigarettes. We successfully applied similar restrictions in previous RCTs for smoking cessation trials conducted by our group.^{132, 133} Healthy age-matched never-smoking/non-vaping volunteers (N=10) will be included for the MRI sub-

study. Healthy volunteers will be never-smoker (<100 cigarettes per lifetime), non-vapers (no use of ENDS on more than 50 occasions and not in the last 12 months), no history of lung disease, no use of inhalation medication and no lung infection in the last four weeks. Most studies define a never-smoker as one who either has never smoked at all or has smoked <100 cigarettes (or the equivalent amount of tobacco) in his or her lifetime, which is in line with that proposed by the World Health Organization. Volunteers will be aged matched to our sub-group of participants who undergo MRI assessments within the RCT. Exclusion criteria are listed under section 7.1. Eligibility criteria. We thrive at limiting the number of exclusion criteria to the minimum to ensure the external validity of the study findings to the general population interested in using ENDS for smoking cessation. We will exclude pregnant or breast feeding women at baseline or intending to become pregnant during the first 6-months of the clinical study; not because ENDS should be particularly harmful in such populations, in particular in comparison to the known harms from smoking tobacco cigarettes for pregnant and breastfeeding women and their fetuses and babies, but because we expect dedicated trials in this population will be conducted by other research teams in the future.

4. STUDY OBJECTIVES

4.1 Overall Objective

The study aims to assess the efficacy, safety and toxicology of ENDS for helping smokers quit smoking or reduce the number of cigarette smoked per day over a 24-month follow-up period with follow-up visits done at 6-, 12- and 24- months.

4.2 Primary Objective

The study seeks primarily to determine the efficacy of ENDS for helping smokers quit smoking or reduce the number of cigarette smoked per day over a 24-months follow-up period with follow-up visits done at 6-, 12- and 24- months.

4.3 Secondary Objectives

Secondary objectives are to assess the effect of using ENDS on exposure to inhaled toxic compounds and assess the effect of ENDS use on health-related outcomes, including clinical health-related outcomes (respiratory symptoms, pulmonary function,, olfactory function, inflammatory biomarkers) and surrogate health-related outcomes (oxidative stress, cardiovascular risk factors, micronuclei in mouth epithelium).

4.4 Safety Objectives

The study aims to assess the safety of ENDS in terms of adverse events.

5. STUDY OUTCOMES

5.1 Primary Outcome

The primary outcome for the main analysis at 6-months follow-up will be the continuous smoking abstinence from target quit date (TQD) to the 6-month follow-up visit, ascertained by self-report (self-report of no smoking from target quit date) and confirmed by urinary level of anabasine (<3 ng/ml).^{1, 34, 35} If anabasine is missing, validation will be done by exhaled carbon monoxide (CO) (<10 ppm).

The primary outcome for the extended follow-ups at 12- and 24-months will be the self-reported 7-day point prevalence abstinence (not having smoked cigarettes within the preceding week), again confirmed by urinary level of anabasine (<3 ng/ml). If anabasine is missing, validation by exhaled carbon monoxide (CO) (<10 ppm).

5.2 Secondary Outcomes

The secondary outcomes are as follows:

- Secondary smoking cessation outcomes:

6 month follow-up:

- Continuous smoking abstinence. Self-report of having smoked no cigarettes from TQD, validated by urinary levels of NNAL (4-(methylnitrosamino)-1-(3-pyridyl)-1-butanol). If NNAL is missing, validation by urinary levels of anabasine or exhaled CO.
- Self-reported smoking abstinence allowing a 2-week 'grace period' after the TQD
- Validated smoking abstinence allowing a 2-week 'grace period' after the TQD, validated by urinary levels of anabasine. If anabasine is missing validation by exhaled CO.
- Validated smoking abstinence allowing a 2-week 'grace period' after the TQD, validated by urinary levels of NNAL. If NNAL is missing, validation by urinary levels of anabasine or exhaled CO.
- Self-reported smoking abstinence allowing up to 5 cigarettes in total after the TQD.
- Validated smoking abstinence allowing up to 5 cigarettes in total after the TQD, validated by urinary levels of anabasine. If anabasine is missing validation by exhaled CO.
- Validated smoking abstinence allowing up to 5 cigarettes in total after the TQD, validated by urinary levels of NNAL. If NNAL is missing, validation by urinary levels of anabasine or exhaled carbon monoxide (CO).
- Self-reported 7-day point prevalence abstinence at 6 months, Self-report of having smoked no cigarettes in the past seven days.
- Validated 7-day point prevalence abstinence. Confirmation of having smoked no cigarettes in the past seven days, validated by urinary levels of anabasine. If anabasine is missing validation by exhaled carbon monoxide (CO).
- Validated 7-day point prevalence abstinence. Confirmation of having smoked no cigarettes in the past seven days, validated by urinary levels of NNAL. If NNAL is missing, validation by urinary levels of anabasine or exhaled carbon monoxide (CO).
- Number of cigarettes smoked per day (CPD), self-reported, at baseline, TQD, phone visits and 6 months visit
- Change in number of cigarettes smoked per day (CPD), self-reported. Successful reduction defined as 50% reduction in CPD.
- Concentrations of urinary TSNAs (NNN, NNK and its metabolite NNAL), VOCs and PAHs (1- and 2-Naphtol and 1-OHP)
- Respiratory symptoms assessed by questionnaire (CAT, mMRC, ACT, ECRHS) ¹³⁴⁻¹³⁷
- Oxidative stress assessed by 8-OHdG and 8-isoprostane concentrations in both EBC and urine
- CVRFs assessed by HDL- and LDL-cholesterol, triglycerides, HbA1c (only for participants with diabetes), creatinine, blood pressure levels, heart rate, waist circumference and body mass index.
- Pulmonary function, measured by conventional pulmonary function tests and by the more

sensitive techniques of multiple breath washout and MRI

- Micronuclei assessment in buccal epithelium
- Olfactory function assessment (olfactory identification score (OIS)). Cut-off for hyposmia 11 points, cut-off for anosmia 8 points.
- "Dry-hit" recognition at 6 month-follow up
- Inflammatory biomarkers

12- and 24- months follow-up:

- Validated 7-day point prevalence abstinence. Confirmation of having smoked no cigarettes in the past seven days, validated by urinary levels of NNAL. If NNAL is missing, validation by urinary levels of anabasine or exhaled CO.
- Validated 7-day point prevalence abstinence. Confirmation of having smoked no cigarettes in the past seven days, validated by urinary levels of NNAL. If NNAL is missing, validation by urinary levels of anabasine or exhaled CO.
- Self-reported 7-day point prevalence abstinence. Self-report of having smoked no cigarettes in the past seven days.
- Continuous smoking abstinence. Self-report of having smoked no cigarettes from quit date, validated by urinary levels of anabasine. If anabasine is missing, validation by exhaled CO.
- Continuous smoking abstinence. Self-report of having smoked no cigarettes from TQD, validated by urinary levels of NNAL. If NNAL is missing, validation by urinary levels of anabasine or exhaled CO.
- Self-reported smoking abstinence allowing a 2-week`grace period'. Smoking abstinence allowing a 2-week`grace period' after the TQD.
- Validated smoking abstinence allowing a 2-week`grace period'. Smoking abstinence allowing a 2-week`grace period' after the TQD, validated by urinary levels of anabasine. If anabasine is missing validation by exhaled CO.
- Validated smoking abstinence allowing a 2-week`grace period'. Smoking abstinence allowing a 2-week`grace period' after the TQD, validated by urinary levels of NNAL. If NNAL is missing, validation by urinary levels of anabasine or exhaled CO.
- Self-reported smoking abstinence allowing up to 5 cigarettes. Smoking abstinence allowing up to 5 cigarettes in total after the TQD.
- Validated smoking abstinence allowing up to 5 cigarettes. Smoking abstinence allowing up to 5 cigarettes in total after the TQD, validated by urinary levels of anabasine. If anabasine is missing validation by exhaled carbon monoxide (CO).
- Validated smoking abstinence allowing up to 5 cigarettes. Smoking abstinence allowing up to 5 cigarettes in total after the TQD, validated by urinary levels of NNAL. If NNAL is missing, validation by urinary levels of anabasine or exhaled CO.
- Number of cigarettes smoked per day (CPD), self-reported.
- Change in number of cigarettes smoked per day (CPD), self-reported. Successful reduction defined as 50% reduction in CPD. Concentrations of urinary TSNAs (NNN, NNK and its metabolite NNAL), VOCs and PAHs (1- and 2-Naphtol and 1-OHP)
- Respiratory symptoms assessed by questionnaire (CAT, mMRC, ACT, ECRHS) ¹³⁴⁻¹³⁷
- SARS-CoV-2 infection through serology and related SAEs
- Oxidative stress assessed by 8-OHdG and 8-isoprostane concentrations in both EBC and urine
- CVRFs assessed by HDL- and LDL-cholesterol, triglycerides, HbA1c (only for participants with diabetes), creatinine, blood pressure levels, heart rate, waist circumference and body mass index.
- Pulmonary function, measured by conventional pulmonary function tests and by the more sensitive techniques of multiple breath washout and MRI
- Micronuclei assessment in buccal epithelium
-
- Olfactory function assessment (olfactory identification score (OIS)). Cut-off for hyposmia 11 points, cut-off for anosmia 8 points.

5.3 Other Outcomes of Interest

Other variables of interest will be assessed by questionnaires:

- Physical activity (International Physical Activity Questionnaire, IPAQ) ¹³⁸
- Withdrawal symptoms (Minnesota Nicotine Withdrawal Scale (MNWS) ^{139, 140}
- Legal and illegal drug use: Alcohol consumption ¹⁴¹, illegal drug use (cannabis, cocaine, other) ¹⁴²
- Sleep quality (Pittsburgh sleep quality inventory PSQI) ¹⁴³
- Quality of life (EQ-5D questionnaire) ¹⁴⁴
- Depression symptoms (PHQ-9) ¹⁴⁵
- Anxiety (GAD-7) ¹⁴⁶
- Environmental pollution exposure (e.g. second hand smoke) ^{147, 148}

5.4 Safety Outcomes

Safety outcome variables are adverse events (AEs) and serious adverse events (SAEs) following international standards. ¹⁴⁹

Safety outcomes are defined as follows:

[figure not shown]
- Adverse events
- ENDS deficiencies

6. STUDY DESIGN

6.1 General study design and justification of design

The ESTxENDS trial is a multicentre, pragmatic, open-label randomized controlled trial with two parallel groups allocated in a 1:1 ratio. The trial will be based on a superiority hypothesis of ENDS + SOC for smoking cessation to SOC alone in adult (≥ 18 years) smokers. The intervention group will receive ENDS and nicotine-containing e-liquids to use *ad libitum* until 6 months visit, plus SOC. The control group will receive SOC only. At the baseline visit, participants in the control group will receive a voucher ("BERNcity Geschenkkard" or similar voucher for Lausanne, Geneva, Zürich and St. Gallen) worth CHF50. The amount of CHF50 is of similar monetary value to what the intervention group will receive in form of the two ENDS devices and the e-liquids. A total of 1172 smokers will be randomized in the study, 586 in each group. Recruitment of the participants is planned to occur over 13-18 months at all 5 study sites. Our main outcome at the 6-month visit will be self-reported continuous smoking cessation after target quit date, with blinded biochemical verification by exhaled carbon monoxide (CO), urinary cotinine, anabasine, VOCs, TSNA (NNN, NNK and its metabolite NNAL) and PAHs (1- and 2-Naphtol and 1-OHP) levels. At the 12-month and 24-month visit, the main outcome will be the self-reported 7-day point prevalence abstinence (not having smoked cigarettes within the preceding week), again all confirmed by the exhaled CO level and the urinary level of cotinine and anabasine. Statisticians and laboratory personnel will be blinded to group allocation. Participants and clinicians will not be blinded. We will use the methodology of a clinical trial investigating a medicinal product to test the efficacy and safety of ENDS.

Figure 6.1-1: ESTxENDS trial design schematic

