

Outcome(s):
	
Primary outcome
 
 - The primary outcome at 6 month will be the continuous smoking abstinence from target quit date to the 6-month follow-up visit, ascertained by self-report (self-report of no smoking from target quit date) and confirmed by urinary levels of anabasine (<3 ng/ml). - The primary outcome at 12- and 24- months will be the self-reported 7-day point prevalence abstinence (not having smoked cigarettes within the preceding week), confirmed by urinary levels of anabasine (<3 ng/ml). 
Secondary outcomes
 
 - Secondary smoking cessation outcome will alternate definitions of the smoking cessation outcome: as the primary outcome, but allowing up to 5 cigarettes in total and a 2-week 'grace period' after the target quit date, self-reported 7-day point prevalence abstinence, all confirmed by urinary level of anabasine. We will also apply alternate definitions of the validation of exposure to tobacco smoking with: exhaled CO levels (CO<10 ppm) and NNAL (<10 pg/ml creat) and exposure to nicotine (from tobacco cigarettes, ENDS or NRTs) with urinary levels of cotinine. We will further report on change in the self-reported number of cigarettes smoked per day (CPD), with 50% reduction in CPD from baseline to follow-up considered as successful reduction. - Concentrations of urinary tobacco-specific nitrosamines (TSNAs), volatile organic compounds (VOCs), aldehydes and polycyclic aromatic hydrocarbons (PAHs) for all participants. Participants will complete a detailed questionnaire to account for other sources of exposure to these chemicals. - Respiratory symptoms (self-report) - Oxidative stress assessed by 8-OHdG and 8-isoprostane concentrations in both exhaled breath condensate (EBC) and urine; - Cardiovascular risk factors (CVRF) assessed by HDL- and LDL-cholesterol, HbA1c, creatinine, blood pressure levels, waist circumference, and body mass index. - Adverse events (AEs), serious adverse events (SAEs) following international standards. - Mood, anxiety and sleep quality (Self report) - Pulmonary function, measured by conventional pulmonary function tests and by multiple breath washout (MBW). - Structural and functional outcomes as ventilation and perfusion of the lung, measured by MRI. - Micronuclei (MN) in buccal epithelium - Olfactory function assessed by the Burghart Sniffin' Sticks (odor identification score (OIS)). - Dry-hit recognition - Detection of inflammatory biomarkers

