11.4.2 Primary Analysis

To answer the primary research question, we will compare the rates of quitting among smokers randomized to ENDS vs. those receiving usual care, on an intention-to-treat basis. Continuous smoking cessation from target quit date will be the main outcome, confirmed by biomarkers of exposure (anabasine). We will calculate quit rates, relative risks (RR), and absolute risks for ENDS +SOC (intervention group) compared to SOC alone (control group). We will further compare groups using multivariate regression models adjusting for appropriate co-variates. Participants who stopped smoking, and who are continuous ENDS users, will be considered quitters.

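### Protocol 6.1 adds cotinine to the confirmation of the main outcomes, in conflict with 5.1, and no SAP settles the rule at 12 and 24 months

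*Supplement*

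**What the plan says.** All references are to protocol 9.0 and SAP 2.0.

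- **Protocol 6.1, 12 and 24 months.** The main outcome is 7-day point prevalence abstinence, "again all confirmed by the exhaled CO level and the urinary level of cotinine and anabasine".
- **Protocol 6.1, 6 months.** The main outcome is self-reported continuous cessation "with blinded biochemical verification by exhaled carbon monoxide (CO), urinary cotinine, anabasine, VOCs", followed by TSNAs and PAHs.
- **Protocol 5.1.** At 6 months abstinence is "confirmed by urinary level of anabasine (<3 ng/ml"). At 12 and 24 months it is "again confirmed by urinary level of anabasine (<3 ng/ml). If anabasine is missing, validation by exhaled carbon monoxide (CO) (<10 ppm").
- **Synopsis, 9.2.1 and 11.4.2.** The synopsis and 9.2.1 give the anabasine rule for all three visits. Section 11.4.2 names anabasine as the confirming marker for the 6-month outcome. None of them uses cotinine to confirm a primary outcome.
- **Meaning of cotinine.** The synopsis assigns it to "exposure to nicotine (from tobacco cigarettes, ENDS or NRTs) with urinary levels of cotinine".
- **Status of vapers.** Section 11.4.2 states: "Participants who stopped smoking, and who are continuous ENDS users, will be considered quitters".
- **SAP 2.0.** Section 6.1 defines the 6-month primary outcome by anabasine, with CO if anabasine is missing. Table 4 places the 12- and 24-month primary outcomes outside the SAP.

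**The concern.** Two sections of the same protocol version give different rules for the same endpoint. Under 6.1 a participant must pass CO, cotinine and anabasine at 12 and 24 months. Under 5.1 anabasine decides alone, and CO is used only when anabasine is missing.

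The difference is not neutral between arms. The intervention supplies nicotine, and the protocol itself says that cotinine picks up nicotine from ENDS or NRT. A cotinine criterion would therefore fail participants whom 11.4.2 counts as successes, and Table 11.2-1 expects most of the vaping quitters in the intervention arm (49 against 11 at 12 months). The bias would run against ENDS.

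At 12 and 24 months no SAP stands behind the protocol to resolve the conflict. SAP 2.0 also records that a study team aware of allocation took over all analyses. In that setting an endpoint definition should not be left with two readings.

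**Working it through.** **Inputs.** Expected quitters per arm from Table 11.2-1 (Ai and Ac use ENDS; Ci and Cc do not):

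| Visit | Ai | Ci | Ac | Cc |
|---|---|---|---|---|
| 6 months | 56 | 50 | 11 | 56 |
| 12 months | 49 | 38 | 11 | 44 |
| 24 months | 37 | 32 | 11 | 26 |

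**Step 1: reproduce the plan.** At 12 months the table leaves 545 followed per arm. (49 + 38)/545 = 87/545 = 16.0% and (11 + 44)/545 = 55/545 = 10.1%, which match the 16% and 10% in 11.2. The two-proportion power for 10% against 16% with 586 per arm is 86.4%, against the stated 86%.

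**Step 2: risk ratio under the 5.1 rule.** The arms are the same size, so the denominators cancel and RR = (Ai + Ci)/(Ac + Cc).

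- 6 months: 106/67 = 1.58
- 12 months: 87/55 = 1.58
- 24 months: 69/37 = 1.86

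**Step 3: risk ratio if cotinine is also required.** Let f be the share of vaping quitters who are cotinine-positive, taken as equal in both arms. The documents do not give f, so it is an assumption and a range is shown.

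RR(f) = [Ci + Ai(1 − f)] / [Cc + Ac(1 − f)]

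| f | 6 months | 12 months | 24 months |
|---|---|---|---|
| 0% | 1.58 | 1.58 | 1.86 |
| 50% | 78/61.5 = 1.27 | 62.5/49.5 = 1.26 | 50.5/31.5 = 1.60 |
| 70% | 66.8/59.3 = 1.13 | 52.7/47.3 = 1.11 | 43.1/29.3 = 1.47 |
| 90% | 55.6/57.1 = 0.97 | 42.9/45.1 = 0.95 | 35.7/27.1 = 1.32 |
| 100% | 50/56 = 0.89 | 38/44 = 0.86 | 32/26 = 1.23 |

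**Step 4: where the direction changes.** RR = 1 at f = [(Ai + Ci) − (Ac + Cc)] / (Ai − Ac).

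- 6 months: (106 − 67)/(56 − 11) = 39/45 = 87%
- 12 months: (87 − 55)/(49 − 11) = 32/38 = 84%
- 24 months: (69 − 37)/(37 − 11) = 32/26 = 123%, so it cannot occur

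**Step 5: what is lost short of that.** At 12 months, with 586 per arm as denominator and losses counted as smokers, power on the table's counts is 82% at f = 0 (87 against 55), 56% at f = 25% (74.75 against 52.25, RR 1.43) and 25% at f = 50%. At f = 100%, 38 against 44 of 586 gives a chi-square p of about 0.49.

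**Limits of the table.** Its 12-month row matches the continuous-abstinence rates (10% and 16%). The main outcome at that visit is 7-day abstinence, for which 11.2 expects 11% and 17% with an unchanged RR. The 24-month row implies 69/528 = 13.1% and 37/528 = 7.0%, while the text of 11.2 expects 12% and 8%. The 24-month ratios above are those of the table.

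**The case against.** The strongest reply is that 6.1 is leftover overview text. The synopsis, 5.1, 9.2.1 and 11.4.2 agree on anabasine, no secondary cessation outcome in 5.2 uses cotinine, and the change history records that validation was moved to anabasine and CO in version 5.0. No cut-off is stated for cotinine, VOCs or PAHs, so 6.1 could not be run as a criterion without adding one. Its 6-month list closely follows the assays that 6.2.2 says are analysed blind, and may describe what is measured rather than what must be passed.

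Much of this stands. Anabasine is evidently the intended rule, and at 6 months SAP 2.0 secures it. It does not remove the conflict at 12 and 24 months. There 6.1 is worded as a joint requirement, it concerns follow-up that was added only in version 7.0, after cotinine had been dropped, and the SAP is silent.

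Three stronger readings are tempting, and the documents do not support them:

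- **That 6.1 would fail every quitter who vapes.** Liquid at 0 mg/ml is offered (3.2), continuing vapers are expected to reduce nicotine (3.5), and no cotinine limit is given. Only nicotine vapers above an unstated limit would fail.
- **That it would reverse the 12-month effect.** Table 11.2-1 holds no cotinine status. A change of direction needs f above about 84%, and even at 100% the difference is far from significant.
- **That NRT use would lower the ratio further.** NRT is allowed in both arms (8.7) and no rates by arm are given, so the direction is unknown. If 6 of the 44 control quitters and no intervention quitters failed through NRT, the counts at f = 100% would be 38 against 38.

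**Conclusion.** The point holds as a conflict in the definition of the main outcomes that has to be reconciled. Followed as written, 6.1 would misclassify quitters who vape nicotine, mostly in the intervention arm, and bias the comparison against ENDS.

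The expected 12-month risk ratio would fall from 1.58 to between 1.26 (half of vaping quitters cotinine-positive) and 0.86 (all of them). The loss is material well before any change of direction. At 24 months the ratio would fall from 1.86 to no lower than 1.23. These figures rest on the counts in Table 11.2-1, on an assumed share f that is equal in both arms, and on ignoring NRT.

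The practical weight lies at 12 and 24 months. It would be wrong to infer that the 6-month primary analysis is compromised, or that the two sections give opposite answers to the trial's question. The first is settled by the SAP. The second holds for point estimates only at high values of f, and not at all at 24 months.

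**What to change.** Replace the verification text in 6.1 with the 5.1 rule for all three visits: anabasine below 3 ng/ml, and exhaled CO below 10 ppm only if anabasine is missing. Add one sentence stating that cotinine, VOCs, TSNAs and PAHs are exposure measures and not criteria for the primary outcome. NNAL, which is one of the TSNAs, stays a validator for the secondary cessation outcomes in 5.2. Any analysis plan written for 12 and 24 months should repeat the same rule.

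The cost is one paragraph in the protocol. No new data, assays or 6-month analyses are needed.
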